11.3.1 Analysis of cost-effectiveness

Within-trial cost-effectiveness of ambulatory care management of acute sickle cell painful crises

For a within trial evaluation, incremental costs and outcomes between the two treatment arms will be compared and an incremental cost-effectiveness ratio (ICER)

will be estimated. Given the two outcomes, additional cost per unit of pain decreased within 6 hours and the additional cost per QALY gained will be estimated. We will assess uncertainty around the ICER using nonparametric bootstrapping with replacement by treatment allocation. The probability of the intervention being cost-effective compared to current usual care will be reported across cost-effectiveness thresholds ranging from 0 to £30,000/QALY gained.²⁰

Cost-effectiveness of ambulatory care management of acute sickle cell pain episodes: impact of prevalence and ambulatory unit size and opening hours

In addition to the within trial evaluation, we will assess the value of wider adoption of the ambulatory care model. The main question the model-based evaluation will address is what is the cost-effectiveness of the ambulatory unit care pathway depending on ambulatory unit size and service configurations and prevalence of sickle cell patients in the area, and over a longer time horizon beyond the 14 days follow-up in the trial. The impact of unit sizes, configuration and demand on cost and costeffectiveness of the new model of care will be assessed. We will develop a Markov model with 10 year time horizon and an annual cycle length. In the ED only care setting, we will assume patients who seek treatment for acute pain episodes will have access only to ED and will be in one of the two states after treatment in ED: hospitalised or discharged. On the other hand, patients with access to ambulatory units will be able to access treatment via ED or ambulatory units. We will assume those treated via ED may transition to being hospitalised, discharged or transferred to ambulatory units. Similarly, those treated via ambulatory units may transition to hospital admission or discharged. We will estimate the transition probabilities between different states using trial data. We will complement trial data with additional data drawing from relevant literature and reports³² as well as extracts of further data from study centres.

12. Ethics

This protocol and any subsequent amendments, along with any accompanying material provided to the patient in addition to any advertising material will be submitted by the Investigator to an Independent Research Ethics Committee. Written Approval from the Committee must be obtained and subsequently submitted to the JRMO to obtain Final R&D approval.

12.1 Annual Safety Reporting

The CI will send an Annual Progress Report to the REC and the Sponsor using the Health Research Authority (HRA) template on the anniversary of the REC "favourable opinion".

13. Public Involvement

The NHS Race and Health Observatory commissioned the development of this research protocol to improve management of acute sickle pain. The study protocol was developed after has been co-designed with input from a patient representative from the Sickle Cell Society. A conference organised by the protocol development group in May 2023 included public involvement from sickle cell disease patients. The National

Sickle Pain Group has two other patient representatives and they have had input in the trial design. The NHS Specialised Commissioning for Adults and Children with Haemoglobinopathies Clinical Reference Group has also support this trial.

14. Data handling and record keeping

14.1 Data management

- A signed protocol and any subsequent amendments
- Sponsor Self-Monitoring template for the trial team to complete on a regular basis as detailed by the Monitoring section
- Current/Superseded Patient Information Sheets (as applicable)
- Current/Superseded Consent Forms (as applicable)
- Indemnity documentation from sponsor
- Conditions of Sponsorship from sponsor
- Conditional/Final R&D Approval
- Signed site agreement
- Ethics/MHRA submissions/approvals/correspondence
- CVs of CI and site staff
- UK regulations (GCP) course certificate of each of trial team
- Delegation log
- Staff training log
- Site signature log
- Screening log
- Enrolment log
- Monitoring visit log
- Protocol training log
- Correspondence relating to the trial
- SAE reporting plan for the study

14.2 Source data

Source data worksheets will be supplied to all recruiting sites by the Trial Manager

The following Case Report Forms to be provided

Initial Consent

- Inclusion/Exclusion Criteria
- Background clinical data
- Usual analgesia protocol
- Date of continued consent
- QoL assessment with EQ-5D-5L
- Resource use CRF including Work Productivity and Activity Impairment
 Questionnaire

 Care giver questionnaire including Work Productivity and Activity Impairment Questionnaire

Presentation with APC

- Inclusion/Exclusion Criteria
- Baseline Clinical Assessment of APC
- QoL assessment with EQ-5D-5L (at presentation and at 6h)
- 1-6 hours Clinical Assessment
- 6-24 hours follow up Clinical Assessment
- APC episode resource use CRF (at end of episode at A&E or ACU)

Follow-up assessment 7-14 days after presentation

- SCAPE questionnaire
- QoL assessment with EQ-5D-5L
- Clinical Assessment
- (14d only) Resource use CRF including Work Productivity and Activity Impairment Questionnaire
- Care giver questionnaire including Work Productivity and Activity Impairment Questionnaire

Follow-up assessment at 28 days after presentation

- QoL assessment with EQ-5D-5L
- Resource use CRF including Work Productivity and Activity Impairment
 Questionnaire
- Care giver questionnaire including Work Productivity and Activity Impairment Questionnaire

SAE Form

CRF's will be in electronic format. Clinical information for the CRF's will be extracted from hospital paper and electronic records, and from study specific patient report forms.

Responsibility for completion of CRF's will be with delegated trial team members and will be supervised and monitored by the CI.

14.3 Confidentiality

The Investigator has a responsibility to ensure that patient anonymity is protected and maintained. They must also ensure that their identities are protected from any unauthorized parties. Information with regards to study patients will be kept confidential and managed in accordance with the Data Protection Act, NHS Caldicott Guardian, The Research Governance Framework for Health and Social Care and Research Ethics Committee Approval.

The Investigator as well as the study team must adhere to these parameters to ensure that the Patient's identity is protected at every stage of their participation within the study. To ensure this is done accordingly, each patient, at time of consent must be allocated a unique screening number by either the PI or a member of the study team

before undergoing any screening procedures. The patients initials (the first letter of their first name and the first letter of their last name) should be used as a means of pseudo-anonymizing parameters. This information should be kept on a screening log, which should be updated accordingly throughout the study. Once the patient has completed screening procedures and is enrolled onto the study, the patient will be allocated a trial number by the PI or delegated trial representative.

If any patient information needs to be sent to a third party (including sponsor) the PI and the study team should adhere to patient pseudo-anonymous parameters.

This includes the patient initials, date of birth, gender as well as the unique study ID/randomisation number. Any information that is to be collected by these third parties will utilize these coded details for any relevant documents as well as maintaining databases.

- No additional identifiable information will be collected from the trial subjects
- The Chief Investigator is the 'Custodian' of the data.
- No patient identifiable details will be transferred outside the EU
- The patient always has rights to revoke their authorization for the use of their PHI.
- The patients will be anonymized with regards to any future publications relating to this study.

14.4 Record Retention and Archiving

During the course of research, all records are the responsibility of the Chief Investigator and will be kept in secure conditions. When the research trial is complete, it is a requirement of the Research Governance Framework and Trust Policy that the records are kept for a further 20 years.

15. Laboratories

Not applicable. No samples will be taken in this study.

16. Interventions and tools

16.1 Techniques and interventions

This study includes an intervention of the location of care provided to patients presenting with acute painful crises. This will a 1:1 randomisation between the ED and ACU.

16.2 Tools

The following tools with be used through-out the study (Section 9):

- Pain score (measured on a 0-10 visual analogue scale) at baseline, then I hr, 2 hrs, 3 hrs, 4 hrs, 5 hrs, 6 hrs⁹
- Quality of Life and Quality-Adjusted Life Year (QALY): EQ-5D-5L (ref)

- Patient satisfaction questionnaire Satisfaction with Treatment for Pain Questionnaire (STPQ)³³
- APC episode resource use CRF
- Resource use CRF including Work Productivity and Activity Impairment
 Questionnaire
- Linked participant HES data (inpatient, outpatient, emergency care and critical care)

16.3 Medicinal product

This study will not be evaluating specific medicinal products

16.4 Other biological or chemical products

This study will not be evaluating such products

17. Safety reporting

17.1 Adverse Events (AEs)

An AE is any untoward medical occurrence in a participant to whom an intervention has been administered, including occurrences which are not necessarily caused by or related to that intervention. An AE can therefore be any unfavourable or unintended sign (including an abnormal laboratory finding), symptom or disease temporally associated with study activities.

17.2 Adverse Reaction (ARs)

An AR is any untoward and unintended response in a participant to an intervention. All adverse events judged by either the reporting investigator or the sponsor as having a reasonable causal relationship to the intervention qualify as adverse reactions. The expression 'reasonable causal relationship' means in general that there is evidence or an argument to suggest a causal relationship.

17.3 Notification and reporting of Adverse Events and Reactions

If the AE is not defined as serious, the AE will be recorded in the study documents and the participant followed up by the research team. The AE will be documented in the participants' source documents, the Case Report Form (CRF), and, where appropriate, medical records.

17.4 Serious Adverse Events (SAEs) or reactions

A serious adverse event (SAE) is defined as an untoward occurrence that:

- Results in death,
- Is life-threatening,
- Requires hospitalisation or prolongation of existing hospitalisation,
- Results in persistent or significant disability or incapacity,
- Consists of a congenital anomaly or birth defect, or
- Is otherwise considered medically significant by the investigator.

SARs will be reported to the REC where in the opinion of the CI the event was serious and:

- Related (it may have resulted from administration of any of the research interventions), and
- Unexpected (the type of event is not listed in the protocol or other Reference Safety Information as an expected occurrence).

17.5 Notification and reporting of Serious Adverse Events

Serious Adverse Events (SAEs) that are considered to be 'related' and 'unexpected' will be reported to the sponsor within 24 hours of learning of the event, and to the REC within 15 days in line with the required timeframe.

SAE will be identified by the trial medical staff All Serious Adverse Event (SAEs) will be recorded in the subjects' notes, the CRF, the sponsor Specific SAE form and reported to the Joint Research Management Office (JRMO) within 24 hours of the PI or co-investigators becoming aware of the event. Nominated medically trained co-investigators will be authorised to sign the SAE forms in the absence of the CI at the co-ordinating site or the PI at the participating sites.

AE's are very common findings in patients with SCD at home or in hospital because of the severe and chronic nature of the condition. For the purposes of this study the following AE's will be documented in the participants' medical notes as per standard of care, but not included on the trial CRF;

- Pain associated with the APC, including hospitalisation.
- Abnormal observations, as these are already being collected on the trial CRF.

If any of the above are classified at severe (CTCAE > 3), then they will be entered on the trail CRF.

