6.4 Secondary endpoints

- Time to first analgesia, defined as time from presentation in ACU or ED to first dose of opioid analgesia administered. (For subjects given parenteral opioid prior to arrival in care unit, e.g. in ambulance, timing will start from one hour after parenteral analgesia given in ambulance, even if subject presents less than one hour after analgesia given in ambulance)
- Adherence to NICE guideline in safety observations (defined as proportion of hourly safety observations (respiratory rate, sedation score) taken within first 6 hours (+/- 30 mins)
- Adherence to care plan in analgesia doses (defined as proportion of analgesia doses given according to protocol within first 6 hours (+/- 30 minutes)
- Fit for discharge by 6 hours after first analgesia (defined as pain score 5 or less for at least 2 consecutive hourly assessments; no requirement for parenteral opioid for at least 2 hours and acceptable oral analgesia protocol available for use at home, NEWS score green for >2 hours, patient able to self-administer oral medication, patient mobile. All the above assessed by physician and agreed with patient)
- Time from first analgesia to fit for discharge (defined as pain score 5 or less for at least 2 consecutive assessments; no requirement for parenteral opioid for at least 2 hours and acceptable oral analgesia protocol available for use at home, NEWS score green for >2 hours, patient able to self-administer oral medication, patient mobile. All the above assessed by physician and patient).
- Cumulative dose of morphine or equivalent opioids in first 6 hours and first 24 hours
- Proportion admitted to hospital from ACU or ED
- Length of hospital stay (for those admitted to hospital), length of hospital stay Patient satisfaction with care assessed using SCAPE questionnaire 14 and 28 days after discharge
- Health economic analyses of comparative patient health-related quality of life, costs and cost-effectiveness of ACU versus ED care from the perspective/s of health and social care (NHS and PSS) and, separately, wider society
 - Costs at 28 days post-randomisation
 - QALY at 28 days post-randomisation
 - Incremental cost-effectiveness ratio

7. Study population

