Patients will not be randomised if:

1. Pain can be managed without the need for hospital attendance.

2. Symptoms suggest a complicated crisis, where additional medical problems need to be managed.

3. ACU is not available at the trial centre.

The procedure for these different eventualities is illustrated in the flow-chart (Appendix 3).

Randomised patients

For randomised patients, their management will be implemented by their health care team for ED or ACU, using their pre-agreed pain management protocol. The trial team will not be responsible for treating the patient, but will have the following responsibilities:

- Confirmation of consent, eligibility and allocation to correct treatment location
- Pain score (0-10 numeric rating scale) at baseline and hourly for first 6 hours
- Collection of the following data:
 - a) Safety data (respiratory rate and sedation score) hourly for first 6 hours (taken from hospital paper or electronic record. Record actual values and percentage of scheduled measurements.
 - b) Adherence to pre-agreed pain management protocol.
 - c) Cumulative opioid dose over the first six hours (from hospital paper drug chart or electronic prescribing record) and duration of episode in ED or ACU (APC episode resource use CRF).
 - d) Whether the patient is admitted or discharged from ED or ACU.
 - e) Any additional analgesic medication and all non-analgesic medication.
 - f) Health economic data (Section 11.3)

- g) Patient satisfaction questionnaire, taken 14 and 28 days after presentation using the SCAPE questionnaire.
- h) Quality of life assessment; using the EQ-5D-5L tool taken on consent, presentation, 6 hours, 14 and 28 days after the presentation.
- i) Length of stay for patients admitted to hospital. Defined as time from the decision to admit, to time patient leaves ward.
- j) Re-attendance rate (within 7 days).
- k) Complication rate (acute chest syndrome, other acute sickle complications, physician diagnosis from discharge summary).
- I) Education/employment/daily activity loss (social determinants of health assessment).
- m) Resource use CRF including Work Productivity and Activity Impairment Questionnaire, collected at consent, 14 days and 28 days follow-up.

Observational Arm

Consented subject may be triaged with an uncomplicated APC, but cannot be randomised for a number of reasons including:

- No trial staff available
- No available space on ACU
- ACU is closed
- Presenting within 6 hours of closure of ACU

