9.6 Schedule of Assessment

See Table 1.

Study event	Screening	Consent and enrollment	Phone triage with APC	ED or ACU with APC	Discharge	Follow up	Follow up						
Study Day			1		1							1.1 douro	20. devie
Study event number	4				1	1	-			10	14	14 days	26 days
	1	4	2 3	4	5	6				10	11	12	13
Study time (nours)				(1	2	: 3	4	+ t	6			
Eligibility	X												
Confirm individual protocol		х	х	х									1
Given patient information sheet	х												1
Informed consent		х											1
Confirm consent			Х										
Demographics ^b		Х											
Medical history ^c		Х	Х										
Confirm inclusion/exclusion criteria			Х										
Confirm eligible APC			Х										
Confirm ED and ACU care available			Х										
Randomisation			Х										
Concomitant medication ^d		Х	Х										
Social determinants of health assessment		Х	Х								Х	Х	Х
EQ-5D-5L °		Х	Х								Х	Х	Х
Satisfaction with care questionnaire ^f		Х									Х	Х	Х
Vital signs ^g				Х	Х	Х	Х	Х	Х	Х	Х		
Pain score ^h				Х	Х	Х	Х	Х	Х	Х	Х	Х	Х
Protocol adherence ⁱ											Х		
Time to. disposition ^j											Х		
Time to readiness for discharge											Х		
Cumulative opiate dose k											Х		
Resource use CRF including Work Productivity and Activity Impairment Questionnaire ^m	r	х									х	x	х
APC episode resource use CRF											Х	Х	Х
Adverse events ⁿ											Х	Х	Х
Length of stay											Х		
Re-attendance												Х	Х
EQ-5D-5L for care givers		Х										Х	Х
Care giver questionnaire including Work Productivity and Activity Impairment Questionnaire		x										x	х

Abbreviations: ED; emergency department, ACU; ambulatory care unit, APC; acute painful crisis.

^a 6 hours, or until discharge if before

^b Age, sex, genotype

^cPast medical history, to include sickle complications

^d Collect information from the paper or electronic drug chart

^e Provide patient with the EQ-5D-5L questionnaire. To complete on presentation and 7 days after presentation.

^f Patient satisfaction questionnaire

^g Hourly for the first 6 hours a per standard of care. These results should be taken from the hospital paper or electronic record. Record actual values and percentage of scheduled measurement

^{*h*} Visual pain score to be taken by dedicated trial team. Score to be taken at baseline and hourly for the first 6 hours

^{*i*} Use the hospital or paper record to confirm adherence to protocol

^{*j*} Was the patient admitted or discharged from ED or ACU

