^{*k*} Cumulative opioid dose over the first 6 hours. Use data from the hospital paper or electronic drug chart.

¹To include, but not limited to; acute chest syndrome, hospital acquired pneumonia, any other significant adverse event CTCAE grade > 3

^m Work Productivity and Activity Impairment Questionnaire

 $^{\it n}$ Record any AEs or SAEs in the 7 days from presentation. Use patient's notes and discharge summary.

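### Section 17.5 keeps abnormal observations off the CRF as adverse events because they are collected already, but the specified collection does not span the 7-day adverse event period, and the severity override read literally omits grade 3

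*Protocol*

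**What the plan says.** Section 17.3 gives the general rule. For a non-serious AE, "the AE will be recorded in the study documents", and the CRF is among the places listed.

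Section 17.5 then makes an exception for two categories, pain from the crisis and abnormal observations. These "will be documented in the participants' medical notes as per standard of care, but not included on the trial CRF". The reason given for the second category is "Abnormal observations, as these are already being collected on the trial CRF". An override follows: "If any of the above are classified at severe (CTCAE > 3), then they will be entered on the trail CRF".

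The collection of observations is described in three places:

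- Section 8, Randomised patients, item (a): "Safety data (respiratory rate and sedation score) hourly for first 6 hours".
- Section 9.6, Table 1: a row for Vital signs, marked at hours 0 to 6 and apparently also at discharge (the table is broken in the text available). Its footnote g begins "Hourly for the first 6 hours a per standard of care" and asks for actual values.
- Section 14.2: a clinical assessment form for hours 6 to 24, and another at the 7-14 day follow-up, with no content given for either.

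Table 1 footnote n sets AE and SAE recording at 7 days from presentation. Footnote l lists events to include, ending with "any other significant adverse event CTCAE grade > 3".

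**The concern.** An exemption from AE recording is reasonable when the same information reaches the database by another route. Here the exemption is open-ended and the other route is not. An abnormal observation can therefore be excluded as an AE because it is supposedly collected, at a time or on a sign for which the protocol specifies no collection. It would then sit in the medical notes and not in the trial data.

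This matters because Section 6.4 treats respiratory rate and sedation score as the safety observations, and opioid exposure is itself an endpoint: "Cumulative dose of morphine or equivalent opioids in first 6 hours and first 24 hours". The two settings may differ in how soon and how much opioid is given, so the safety comparison should rest on one recording rule applied everywhere. The override could act as a safety net, but its wording leaves grade 3 in doubt.

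**Working it through.** The point involves no sample size, power or error rate. The check sets the passages side by side and follows each kind of observation through the rules.

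**Time and signs**

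- Exemption (17.5): any observation, any time.
- Specified hourly collection (Section 8(a), Table 1 footnote g): the first 6 hours.
- Signs: two in Section 8(a); an undefined set under Vital signs in Table 1.
- Between 6 and 24 hours: a CRF page exists, content not stated.
- AE period (footnote n): 7 days, which is 7 × 24 = 168 hours.

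Even if the 6-24 hour page captured every observation, which is an assumption, the stated collection would end well before the AE period does, apart from a discharge reading and whatever the 7-14 day assessment holds. The reason for the exemption is therefore not shown to hold for the whole period to which the exemption applies.

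**Routes for a given observation or event**

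1. Abnormal respiratory rate or sedation score in hours 0 to 6: the value is on the CRF. The reason holds.
2. Abnormal oxygen saturation or temperature in hours 0 to 6: on the CRF if Vital signs includes them, not if Section 8(a) is the full list. Both serve as exclusion markers in Section 7.2, so they are charted at entry, but the protocol does not settle whether later values are collected.
3. Non-serious abnormal sedation score at hour 9, grade 3 or lower: exempt as an AE. It reaches the CRF only if the 6-24 hour page asks for it.
4. The same finding on a ward after 24 hours: exempt as an AE, with no specified collection apart from a possible discharge reading or the 7-14 day assessment. It may reach only the notes.
5. Over-sedation or respiratory depression diagnosed as an event: not an observation, so 17.3 applies and it goes on the CRF.
6. Acute chest syndrome: collected by name in Section 8(k) and in footnote l. Hospital-acquired pneumonia is named in footnote l.
7. Anything serious under 17.4, including what the investigator judges medically significant: on the CRF and the SAE form at any grade.

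The gap is confined to routes 3 and 4, and to route 2 if the shorter list of signs governs.

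**The override**

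The sentence pairs the word severe with a grade greater than 3. Taken literally, grade 3 does not satisfy it. Footnote l carries the same sign, so this is not a slip in one place only. A greater-or-equal sign lost in the conversion from PDF cannot be ruled out.

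**The case against.** The strongest case on the other side is that little of importance escapes. Only observations are exempt, not diagnoses. Serious and medically significant events have no grade threshold. Acute chest syndrome and pneumonia are captured by name, and the notes keep the rest. This stands, and it sets the limit of the point.

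A reader might infer more than the protocol supports:

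- **That only two signs are collected, for 6 hours.** Table 1 is broader, the 6-24 hour form exists, and the NEWS score is needed for the fit-for-discharge endpoints. The content is unclear, but that does not show the data are absent.
- **That grade 3 opioid and respiratory events disappear from the trial.** Routes 5 to 7 contradict this. What may be missed is the non-serious abnormal observation.
- **That the ratio of monitored hours to AE hours measures what is missed.** It does not. Discharged patients are at home without charted observations, and events are not spread evenly over time.
- **That the override adds nothing beyond SAE reporting.** This depends on CTCAE grade definitions that the protocol does not give.
- **That 17.3 and 17.5 contradict each other.** 17.5 is an explicit exception to a general rule. Likewise, footnote l is a non-exhaustive list, so its threshold is not a cut-off for recording AEs.
- **That the rule favours one arm.** It applies equally to both, and the protocol states no plan to draw a conclusion of no safety cost from it.

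The objection does not supply a reason for an exemption without a time limit. Nor does the medically significant route replace a uniform rule, since it rests on the investigator's judgement in an open trial.

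**Conclusion.** The point holds in a narrow form. The reason given in 17.5 is not shown to be true beyond the scheduled collection, and the override as printed does not reach grade 3. Followed exactly, the protocol allows non-serious abnormal observations up to grade 3 that fall outside scheduled collection to remain in the medical notes only.

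The size cannot be stated as a number of events, because the protocol gives no rate of abnormal observations and no content for the 6-24 hour and 7-14 day forms. If those forms record all relevant signs, the gap shrinks to the times they do not cover. If the printed sign should be greater-or-equal, the gap is limited to findings below grade 3. The mismatch between an open-ended exemption and a time-limited collection remains in both cases. It is a modest weakness in the safety data and has no bearing on the primary analysis.

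**What to change.** Three wording changes:

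1. In 17.5, limit the exemption to observations whose values are actually entered on the CRF. Any other abnormal observation judged to be an AE then follows 17.3.
2. In 17.5 and in Table 1 footnote l, replace the threshold with CTCAE grade 3 or above, after checking the source file for a lost sign.
3. Reconcile Section 8(a), the Vital signs row with footnote g, and the 6-24 hour form in Section 14.2, so that all three state the same signs and the same duration of collection.

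The cost is small. The values come from charts that the trial team already reads, and the downside is somewhat more AE entries. Sample size, endpoints and patient care are unaffected.
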